The Impact of Frailty on the Postoperative Outcomes of Gastric Cancer Surgery (TOREGA)

05/16/2018

SUMMARY

Background. Gastric cancer is an important health care problem even though treatment advances, and it is diagnosed mainly in elderly. Surgery is the main treatment for gastric cancer and is associated with a high rate of postoperative complications and mortality, even higher in older patients. Chronological age seems not to be the main factor influencing the worse outcome of older patients, comorbidities and frailty have also been taken into account recently.

Methods. Participation in the study will be offered to all centers that are currently part of the Spanish EURECCA (EUropean REgistry of Cancer CAre) Esophagogastric Cancer Registry. The impact of the frailty on different outcome variables will be evaluated. The main outcome variable will be 90-day mortality after the intervention. Health-related quality of life (HRQoL) will also be evaluated.

Objective. The objective of the study is to value the impact of frailty on gastric cancer surgery outcomes therein the Spanish EURECCA Esophagogastric Cancer Registry.

Introduction

Gastric cancer is the fifth most frequent cancer and the third cause of death due to cancer. The increase in life expectancy cause it to be diagnosed more and more in elderly people, with an average age at diagnosis of 68 years in the West (1, 2).

Surgery is the main treatment for gastric cancer and is associated with a high rate of postoperative complications and mortality, which is even higher in elderly patients (data from the ACS-NSQIP between 2007 and 2013: 30-day severe morbidity from 16.3% in 80 years and 30-day mortality from 1.2% in 80 years) (3).

Generally, advanced chronological age is considered a negative prognostic factor for complications and hospital stay in major surgery (4). Age per se, however, seems to be responsible only in part for the increased risk of postoperative complications (5).

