Therefore, it is important to identify fragile patients to implement prevention programs through global geriatric assessments (CGA Comprehensive Geriatric Assessment). Just by having more clinical attention for more fragile patients after major surgery there can be better results of short and long-term postoperative mortality (22). Likewise, as demonstrated in randomized clinical studies, prehabilitation and global geriatric assessment programs improve the results in terms of postoperative complications and hospital stay (30, 31, 32).

The CGA is an established method to evaluate and optimize the physical state, the psychological, functional and social problems in elderly patients in order to improve the results of the treatments. It implies an interdisciplinary evaluation of multiple domains, followed by planning for analysis, treatment, rehabilitation and long-term follow-up (33).

This allows, in the first place, to intervene before an operation, to increase the physiological reserve of a patient, especially with exercise and nutrition (34, 35). In addition, the therapeutic decision can be guided by adapting the surgical recommendations to the physiological capacity of the patient; second, the knowledge of the increased risk of complications and the possible need for transfer to institutions (especially in patients who live alone) prepares patients and their families for postoperative evolution (8).

The majority of studies published in the literature on the relationship between frailty and postoperative results are retrospective studies, which evaluate populations of patients undergoing major surgery and who, in general, analyze short-term results (30-day mortality) (12, 20, 22, 24, 25, 26, 27, 28, 29). None of these takes into account the impact of surgery on the quality of life of this group of patients. Among all these studies there is very little information about the influence of frailty in gastric cancer surgery. There is only one retrospective study that focuses only on gastric cancer surgery, using the Groningen index and revealing an increase in in-hospital mortality and serious complications (Clavien-Dindo complications score ≥ 3) in fragile patients (25). Objective

The aim of the present study is to assess the impact of frailty on the results of gastric cancer surgery (long-term postoperative morbidity and mortality, hospital stay, readmissions, need of transfer to institution of medium or long stay and quality of life).

Methods

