Primary and secondary variables The impact of the frailty on different outcome variables will be evaluated. The main outcome variable will be 90-day mortality after the intervention. Other secondary outcome variables will also be evaluated: incidence of serious complications (Clavien-Dindo complications score ≥ 3), Complication Comprehensive Index (CCI) score (37, 38), hospital stay, incidence of death in patients suffering from a complication (failure to-rescue), hospital readmission within the first 30 days after the discharge, destination of the patient after discharge from hospital [home, social health centers, or geriatric residence], mortality at 12 months after the intervention, quality of life before the intervention and at 12 months.

Frailty evaluation For the assessment of frailty (frailty screening), two questionnaires will be used:

- Questionnaire G8: This is a questionnaire with 8 questions, easy to use, with a total score that varies from 0 to 17 points. Previous studies suggest the score ≤ 14 as a cut-off point to identify the fragile patient, with a sensitivity of 92% and specificity of 52% (36).
- Modified frailty index: This index was described by Velanovich et al. (14), based on a previously validated simplification of the frailty index CSHAFI (Canadian Study of Health and Aging Frailty Index), which was specifically designed to analyze data included in the National Surgical Quality Improvement Program of the American College of Surgeons (ACSNSQIP). It consists of 11 questions with 1 point assigned to each of them on the functional, endocrine, respiratory, cardiovascular and neurological status of the patient. It allows to divide the patients into 4 groups: without frailty (FI = 0), slightly fragile (FI = 1), moderately fragile (FI = 2) and severely fragile (FI ≥ 3).

Postoperative complications Postoperative complications will be classified according to the recommendations proposed by the European Chapter of the International Gastric Cancer Association (EGCA) (unpublished data), its severity through the classification of Clavien-Dindo and the CCI (37, 38). In particular, the CCI will be calculated using the free application that can be found on the website: www.assessurgery.com/calculator_single/.

[Health-related quality of life](#)

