Health-Related Quality of Life (HRQoL) will be evaluated with the validated Quality of Life questionnaires of the European Organization for Research and Treatment of Cancer (EORTC-QLQ), QLQ-C30 (30 items Core Quality of Life Questionnaire, version 3.0) and with the specific module for gastric cancer QLQ-STO22 (22 items Stomach Quality of Life Questionnaire).

- The EORTC-QLQ-C30 is a questionnaire that reflects the multidimensionality of HRQoL in patients with cancer. It is composed of 30 questions distributed in five functional scales (physical, role, cognitive, emotional and social), three scales of symptoms (fatigue, pain and nausea and vomiting), a global health scale and a series of additional questions to evaluate symptoms commonly referred by patients diagnosed with cancer (dyspnea, loss of appetite, insomnia, constipation and diarrhea) and the perceived financial impact.
- The EORTC-QLQ-STO22 questionnaire contains 22 structured items in five domains (dysphagia, food restrictions, pain, reflux and anxiety) and four specific items (dry mouth, alteration of taste perception, body image and hair loss) related to the symptoms of the disease.

Sample size

The calculation of the sample size is based on the primary objective of comparing fragile versus nonfragile patients with respect to postoperative mortality at 90 days after the intervention. Based on mortality data previously published in a retrospective study by Mosquera et al. (24), it is estimated that mortality for the group of non-frail patients is 0.6% and for the group with frailty 4.3%. From the data of the literature, a prevalence of 23% of frailty is calculated in the population of patients with gastric cancer and age \geq 70 years undergoing gastrectomy (24). For a power of 80% and a level of significance of 95% in a unilateral analysis, it is estimated that 276 non-fragile patients and 92 fragile patients would be needed to detect as statistically significant the difference between the proportion of patients who die between both groups.

Statistical analysis plan

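### The 0.6% and 4.3% mortality rates behind the sample size are not shown to be 90-day rates after gastric cancer surgery, so the stated 80% power is unsupported for the primary endpoint

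*Combined protocol and SAP*

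**What the plan says.** Primary and secondary variables sets the endpoint: "The main outcome variable will be 90-day mortality after the intervention". Sample size says the calculation compares frail with non-frail patients "with respect to postoperative mortality at 90 days after the intervention". The rates are introduced with "Based on mortality data previously published in a retrospective study", namely reference 24, and then: "it is estimated that mortality for the group of non-frail patients is 0.6% and for the group with frailty 4.3" per cent. The same paragraph credits reference 24 with a frailty prevalence of 23% among gastric cancer patients aged 70 or over having gastrectomy. It arrives at 276 non-frail and 92 frail patients for 80% power in a one-sided test.

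The Introduction describes most of the published frailty studies as retrospective, in patients having major surgery, and says that they "in general, analyze short-term results (30-day mortality) (12, 20, 22, 24, 25, 26, 27, 28, 29". Reference 24 is in that list. It then adds: "There is only one retrospective study that focuses only on gastric cancer surgery". That study is reference 25.

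**The concern.** The calculation is labelled as a 90-day calculation, but its inputs have no horizon attached. The protocol's only other description of their source points to a shorter horizon and a broader surgical population. No step carries the rates from the source to 90 days or to this population. The Introduction presents short horizons and scarce gastric data as gaps in the literature, and the plan then takes its rates from that literature without comment.

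The plan expects fewer than six deaths (276 × 0.006 = 1.7 non-frail and 92 × 0.043 = 4.0 frail). With so few events, modest changes in the assumed rates move power a long way. What is at stake is whether 368 patients is adequate, ample or far too few for the main comparison.

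**Working it through.** **Inputs from Sample size.** p0 = 0.006 (non-frail), p1 = 0.043 (frail), n0 = 276, n1 = 92. The test is one-sided, and the stated significance level of 95% is read as alpha = 0.05. The difference is 3.7 points and the ratio is 4.3 / 0.6 = 7.17.

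**Formula (pooled normal approximation).** p̄ = (n0·p0 + n1·p1) / (n0 + n1); S0 = √[p̄(1 − p̄)(1/n0 + 1/n1)]; S1 = √[p0(1 − p0)/n0 + p1(1 − p1)/n1]; power = Φ{[(p1 − p0) − 1.645·S0] / S1}.

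**Step 1: the plan's own figure.** p̄ = (1.656 + 3.956) / 368 = 0.01525, S0 = 0.01475 and S1 = 0.02165. Then (0.037 − 1.645 × 0.01475) / 0.02165 = 0.588, and power = 72%. For 80% power at 3:1 the same formula needs 364 + 122 = 486 patients, so 276 + 92 is not reproduced. Two routes come close. Exact enumeration of the uncorrected score test gives 79.8% power, but with a true type I error of about 8% at a common mortality of 1.5%. A one-sided alpha of 0.10 gives 278 + 93. Fisher's exact test gives 61%. This shortfall exists at the plan's own rates. It is a separate matter from the horizon.

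**Step 2: 90-day rates that differ from the planning rates.** The documents give no 90-day gastric rates by frailty, so every rate below is an assumption. All rows use 276/92 and one-sided 5%.

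| What carries over | Non-frail v frail | p̄ | S0 | S1 | z | Power |
|---|---|---|---|---|---|---|
| Difference (3.7 points) | 1.2% v 4.9% | 2.1% | 0.01736 | 0.02344 | 0.360 | 64% |
| Difference | 2.0% v 5.7% | 2.9% | 0.02029 | 0.02560 | 0.142 | 56% |
| Difference | 3.0% v 6.7% | 3.9% | 0.02338 | 0.02802 | −0.052 | 48% |
| Ratio (7.17) | 0.9% v 6.45% | 2.3% | 0.01800 | 0.02623 | 0.987 | 84% |
| Ratio | 1.2% v 8.6% | 3.1% | 0.02070 | 0.02996 | 1.334 | 91% |
| Ratio | 2.0% v 14.3% | 5.1% | 0.02642 | 0.03746 | 2.123 | 98% |

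In the three difference rows, 80% power at 3:1 would need 628, 811 and 1,035 patients in total.

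Counts are sparse, so the normal figures are approximate. Exact enumeration keeps the pattern: 2.0% v 5.7% gives 56% (score test) or 41% (Fisher), and 1.2% v 8.6% gives 95% or 89%.

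**Step 3: the overall rate that the plan implies.** At 23% frail: 0.77 × 0.6 + 0.23 × 4.3 = 1.45%. At the planned 25% frail (92/368): 0.75 × 0.6 + 0.25 × 4.3 = 1.53%. Roughly 1.5% is therefore the figure to compare with the registry.

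**Step 4: what an overall rate can settle.** The rows 2.0% v 5.7% and 1.2% v 8.6% have nearly the same overall mortality (2.9% and 3.1%) but powers of 56% and 91%. An overall rate shows whether the planning figures are at the right level. It does not fix the power, because the split between groups matters as much.

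**The case against.** The strongest reply is that nothing in the protocol says the two rates are 30-day rates. The Introduction speaks of most studies, and of what they do in general. Its list has exceptions: the titles of references 12 and 22 report 1-year and 30-, 180- and 365-day outcomes, and reference 25 is the gastric-only study. Sample size also ties reference 24 to gastrectomy patients aged 70 or over, so a gastric subset of that study is possible. This stands. A reader might infer that the rates are 30-day, mixed-surgery rates and that the stated power is therefore for another endpoint. The documents do not support that, because membership of a hedged list proves neither horizon nor population.

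Two other tempting arguments also fail. A reader might set the 0.6% against the Introduction's "30-day mortality from 1.2% in 80 years". That sentence is damaged in the available text, its age band is lost, and it does not describe non-frail patients, who could be expected to lie below an all-patient rate. A reader might also say that a null result would be uninterpretable. The plan reports an odds ratio, and the precision of that estimate informs a null result whatever rates were assumed.

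What the reply leaves untouched is that horizon, population and a step to 90 days are all absent, for the only mortality inputs to the primary calculation.

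**Conclusion.** The concern holds as a lack of support, not as a demonstrated mismatch. The protocol does not show that 0.6% and 4.3% are 90-day rates after gastric cancer resection in patients aged 70 or over, and its own background gives reason to ask. The 80% power is therefore unsupported for the primary endpoint. The direction of any error is unknown: over the ranges shown, power is 48% to 64% if the absolute difference carries over and 84% to 98% if the ratio does. These figures rest on assumed rates, the pooled normal formula, one-sided alpha of 0.05, the planned 276/92 split and no losses. The 72% at the plan's own rates is not evidence about the horizon, but it means that the power statement needs revising in any case.

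**What to change.** 1. State the time horizon and surgical population behind the two rates. If they are 90-day gastric rates, one sentence settles the question of horizon and population.
2. Obtain from the registry the overall 90-day mortality after potentially curative gastrectomy in patients aged 70 or over, and compare it with the implied 1.5% or so. Study design describes the registry as holding prospective, validated data on operated patients, and Work plan says that follow-up is already collected there.
3. The registry is not shown to hold the frail/non-frail split, since Data collection puts the frailty questionnaires in a new database. Set the two group rates as explicit assumptions that reproduce the registry's overall rate.
4. Restate the power at 368 patients in a short table with both constant-difference and constant-ratio rows, naming the formula used.

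The cost is one registry query and a rewritten paragraph. The stated power may move in either direction.

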Study design: Patients and participating Centers This is a prospective and multicenter cohort study, within the Spanish EURECCA Esophagogastric Cancer Project, to investigate the impact of frailty on the postoperative results of surgery for gastric cancer in elderly patients. Inclusion/exclusion criteria will be following:

- Inclusion criteria: Patients ≥ 70 years diagnosed with gastric cancer (whether or not they have received neoadjuvant treatment) and candidates for elective surgical resection with potentially curative intention (R0) even if it is finally an R1 or R2.
- Exclusion criteria: Patients with disseminated gastric cancer or candidates for palliative surgery, as well as those patients who do not give their consent to participate. Participation in the study will be offered to all centers that are currently part of the Spanish EURECCA Esophagogastric Cancer Registry. Those hospitals that show their desire to participate must sign the Letter of Commitment.

The Spanish EURECCA Upper GI Cancer Group was created in 2012 and collects prospective and validated information about all the patients submitted to surgery for esophagogastric cancer in the public hospitals of four Spanish Autonomous Communities, with the aim of having reliable information on the results of this surgery and constitute a platform for the development of research projects.

Data collection

A specific on-line database will be created for this project, with all the security measures (user and password for individual access), in which the researchers will record the data referring to the Frailty and Quality of life questionnaires. On this basis, the researcher will use the patient identifier (random 6-digit code) previously established by the on-line registration of the EURECCA Project where the patients variables are usually collected.

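### The group sizes assume 25% frail although the same paragraph states 23%, and the stated 80% power depends on an unnamed formula

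*Combined protocol and SAP*

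**What the plan says.** The Sample size section sizes the study for "comparing fragile versus nonfragile patients with respect to postoperative mortality at 90 days after the intervention". It assumes "mortality for the group of non-frail patients is 0.6% and for the group with frailty 4.3"%, both taken from a published retrospective study. It then states "a prevalence of 23% of frailty is calculated in the population of patients with gastric cancer", restricted to those aged 70 or over having gastrectomy. The target power is 80%, with "a level of significance of 95% in a unilateral analysis". The result is that "it is estimated that 276 non-fragile patients and 92 fragile patients would be needed".

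The section does not write a total, name the formula or test, describe recruitment by frailty status, or explain how a 23% prevalence led to these two group sizes. On design, the Methods state: "This is a prospective and multicenter cohort study". Under Work plan, frailty is scored after the tumour committee has met, so that the score does not change the treatment decision.

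**The concern.** Two figures in one paragraph disagree. The group sizes give 92/(276 + 92) = 25.0% frail, and the stated prevalence is 23%. In a trial with allocation the ratio could be chosen. Here patients enter on age, diagnosis and surgical intent, and the frail share is whatever the population supplies, so the split has to follow the prevalence assumption.

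The frail group matters most for power. On the plan's rates it contributes about 92 × 0.043 = 4.0 of the expected deaths, against 276 × 0.006 = 1.7 in the non-frail group. With five or six deaths in all, a reader of a null result will lean on the stated power, so it should be clear what that figure rests on. As written it cannot be checked without guessing the formula and reinterpreting a significance level of 95%.

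**Working it through.** **Inputs (all from Sample size).** Mortality p0 = 0.006 (non-frail) and p1 = 0.043 (frail), so d = 0.037; power 80%, z = 0.842; prevalence 23%; groups 276 and 92. I read the significance level as one-sided 5%, z = 1.645.

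**1. Reproducing the plan's figure.** With one pooled variance and a 3:1 ratio:

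- Pooled mortality = (3 × 0.006 + 0.043)/4 = 0.01525.
- Non-frail n = 0.01525 × 0.98475 × 4 × (1.645 + 0.842)² / 0.037² = 271.3, so 272.
- Frail n = 271.3/3 = 90.4, so 91.

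The total is 363, within 2% of 276 + 92 = 368. Other formulas at 3:1, one-sided, do not come close: two-variance (Fleiss) 364 + 122 = 486; the same with continuity correction 466 + 156 = 622; arcsine about 358 + 119; unpooled about 584 + 195.

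**2. The split at the stated prevalence.**

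- Expected frail in 368: 0.23 × 368 = 84.6, about 85, leaving 283 non-frail.
- Binomial(368, 0.23): central 95% range 69 to 101; probability of at least 92 is 19.7%.
- Total at which 92 frail are expected: 92/0.23 = 400 (308 + 92).

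**3. Re-solving the formula of step 1 at 23:77.** Pooled mortality = 0.77 × 0.006 + 0.23 × 0.043 = 0.01451. Non-frail n = 0.01451 × 0.98549 × (1 + 77/23) × (1.645 + 0.842)² / 0.037² = 280.8, so 281. Frail n = 280.8 × 23/77 = 83.9, so 84. Total 365.

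**4. Power, one-sided 5%.** Let SE0 be the standard error from the pooled mortality and SE1 the one from the two separate mortalities.

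- Single pooled variance: Φ(d/SE0 − 1.645). At 276/92, SE0 = 0.01475, so Φ(2.508 − 1.645) = 80.6%.
- Two-variance: Φ((d − 1.645 × SE0)/SE1). At 276/92, SE1 = 0.02165, so Φ((0.037 − 0.02427)/0.02165) = Φ(0.588) = 72.2%.
- Exact: binomial enumeration of the rejection region.

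| Calculation | 276/92 | 283/85 | 308/92 |
|---|---|---|---|
| Single pooled variance | 80.6% | 80.3% | 83.1% |
| Two-variance normal | 72.2% | 71.3% | 73.6% |
| Uncorrected chi-square, enumerated | 79.8% | 75.7% | 77.5% |
| Fisher's exact test | 61.2% | 55.3% | 58.9% |

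The true one-sided type I error of the uncorrected chi-square, at the pooled mortality, is 8.1% at 276/92 and 6.8% at 283/85.

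**5. How much is due to the split.** From 276/92 to 283/85 the loss is 0.3 points (single pooled variance), 0.9 (two-variance), 4.1 (enumerated chi-square) and 5.9 (Fisher). The exact figures move in steps: the enumerated chi-square has lower power at 308/92 than at 276/92, despite 32 more patients and the same number frail. Averaged over the random split of 368 patients, its power is 75.8% at 23% prevalence and 76.7% at 25%, about one point apart.

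**The case against.** The best defence is that 3:1 is a rounding of 23:77 and nothing follows from it. On the formula that comes closest to the plan's figures, the correct split needs 281 + 84 = 365 patients, so 368 still suffices and 92 frail is no longer required. Two percentage points are also small beside the 10.4 to 56.0% frailty range that the Introduction gives for candidates for elective surgery. This largely stands: the mismatch is minor in its effect on power. It does not make the paragraph consistent, because the rounding is not stated and 92 is presented as the number needed.

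Three stronger readings are tempting, and the documents do not support them.

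- *That 368 patients will fail to give 92 frail.* The plan writes no total and no stopping point; 368 is the sum of the two groups, which could be read as minimums. Even at 368, reaching 92 has about a 20% chance.
- *That the mismatch brings power down from 80% to 71%.* The two-variance formula already gives 72% at the plan's own 276/92. About 8 of those 9 points come from changing formula.
- *That 400 patients would restore 80%.* They restore the expected frail count, but power is 73.6% by the two-variance formula, 77.5% by enumeration and 58.9% by Fisher.

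The defence can add that a significance level of 95% beside a one-sided test plainly means 5%. I agree; it is a wording slip and adds nothing to the arithmetic.

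**Conclusion.** The inconsistency is real. The paragraph's group sizes do not follow from its own prevalence, and the implied cohort is expected to be about 7 frail patients (8%) short of the number it calls necessary. Its effect on power is small.

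The larger matter is that 80% is approximately reproduced in only two ways: by an approximation that applies one pooled variance under the alternative as well, or by an uncorrected chi-square whose true type I error at 276/92 is about 8% instead of 5%. The standard two-variance formula and Fisher's exact test fall well below 80% at either split.

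This rests on one-sided 5%, on the plan's mortality rates and prevalence, and on enrolment without regard to frailty status. All the powers are for an unadjusted comparison of two proportions, as in the sample size paragraph. The Statistical analysis plan specifies adjusted logistic regression for 90-day mortality, and none of these figures is the power of that model.

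**What to change.** Rewrite the Sample size paragraph so that its figures agree:

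- State the total and the split at the stated prevalence: 368 patients, with 85 frail and 283 non-frail expected.
- Name the formula or test and give the power that it yields at that split: about 71% by the two-variance normal formula, or about 80% only if the single-pooled-variance approximation is named as such.
- Write the error rate as significance level 5%, one-sided.

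If 92 frail patients is meant as a fixed requirement, say so and note that it corresponds to an expected total of 400, without presenting that total as giving 80% power on the two-variance or exact calculations.

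The cost is one paragraph of wording. No extra enrolment or change of design is needed; unless the approximation is kept and named, the stated power becomes less favourable.

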The characteristics of fragile and non-fragile patient groups will be compared through frequency tables. The Chi-square test will be used to compare the differences between the categorical variables and the ANOVA test for the continuous variables. Different analyzes are proposed according to the study variables that are to be analyzed. For dichotomous type response variables (90- day mortality, 12-month mortality, incidence of serious complications, incidence of in-hospital death in patients with complications, and hospital readmission at 30 days after discharge), a multivariate logistic regression will be used to evaluate the risk (odds ratio) of these variables. For continuous response variables (ICC score) at 30 days after the intervention, and number of days of hospital stay), linear regression models will be used. For the variable categorical response of the patient after hospital discharge, an ordinal logistic regression model will be done. All regression models will be adjusted for age, sex, body mass index (BMI), type of gastrectomy, center volume, neoadjuvant treatment and degree of frailty. Regarding HRQoL analysis, the mean scores and 95% confidence intervals for the different domains of preoperative HRQoL and one year after surgery will be calculated. Changes of more than 10 points on a scale from 0 to 100 will be considered clinically relevant as previously suggested in other publications (40). Work plan The study period includes: Patient recruitment. Follow-up for 1 year to meet the objectives of the study.

The study starts by assessing the fragility of the patients. Once the stage study is completed, the potential curative surgery is determined and after the case presentation in the Multidisciplinary Tumor Committee of each institution, the G8 questionnaires and modified fragility index will be carried out to identify the state and degree of fragility, 2 weeks prior to surgery. The result of the evaluation of the frailty of the patient, will be performed after the Multidisciplinary Committee, thus it will not modify the therapeutic decision.

To measure the Health Related Quality of Life (HRQoL), the QLQ-C30 and QLQ-STO22 questionnaires, will be delivered at the time of the preoperative visit and 12 months after surgery.

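### 276 non-frail and 92 frail patients do not give the stated 80% power at one-sided 5%: the usual formula gives 72%, and the exact tests examined that hold 5% give 61% to 67%

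*Combined protocol and SAP*

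**What the plan says.** The Sample size section of the combined protocol and SAP bases the cohort size on comparing 90-day mortality between frail and non-frail patients.

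- Assumed rates: "it is estimated that mortality for the group of non-frail patients is 0.6% and for the group with frailty 4.3" (per cent).
- Error rates: "For a power of 80% and a level of significance of 95% in a unilateral analysis".
- Prevalence: "a prevalence of 23% of frailty is calculated in the population of patients with gastric cancer" aged 70 or over having gastrectomy.
- Result: "it is estimated that 276 non-fragile patients and 92 fragile patients would be needed".

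The section names no formula, software or test. The Statistical analysis plan section mentions the chi-square test when describing group characteristics. For the dichotomous outcomes, 90-day mortality among them, it says that "a multivariate logistic regression will be used to evaluate the risk (odds ratio) of these variables". It does not say there whether the comparison is one-sided or two-sided.

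**The concern.** Mortality of 0.6% and 4.3% in groups of 276 and 92 means about 1.7 and 4.0 deaths. With so few events, sample-size formulas that look alike give very different answers, and a test's nominal level can be far from its true level. An unnamed formula that lands on 80% therefore needs checking.

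The 80% figure is the only justification the plan gives for the cohort size. If true power is well below it, a non-significant primary result could be read as adequately powered evidence that frailty does not matter. If the power is recovered only through a test that exceeds 5%, a significant result would carry more false-positive risk than the plan states.

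**Working it through.** **Inputs (all from the Sample size section).** p1 = 0.006, p2 = 0.043, difference d = 0.037; n1 = 276, n2 = 92, ratio 3:1; power 80%. The level written as 95% is read as one-sided alpha = 0.05. So z(alpha) = 1.645, z(beta) = 0.842 and (1.645 + 0.842)² = 6.183. The weighted mean rate is (3 × 0.006 + 0.043)/4 = 0.01525.

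**1. Reproducing 276/92.** Use one pooled variance in both the alpha and the power term: n2 = 6.183 × V × (1 + 1/3)/d².
- Poisson variance, V = 0.01525: n2 = 91.8, n1 = 275.5. Rounded up, this is 276/92, with nominal power 0.801.
- Binomial variance, V = 0.01525 × 0.98475: n2 = 90.4, n1 = 271.3.

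The Poisson version matches exactly. That it is the source is an inference from the match.

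**2. Why the shortcut fails here.** It assumes that the difference is no more variable under the planned rates than under the null.
- SE under the null: √[0.01525 × 0.98475 × (1/276 + 1/92)] = 0.01475.
- SE under the planned rates: √[0.006 × 0.994/276 + 0.043 × 0.957/92] = 0.02165.
- Variance ratio: (0.02165/0.01475)² = 2.15.

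**3. Usual formula (null variance for alpha, alternative variance for power).** Power = Φ[(0.037 − 1.645 × 0.01475)/0.02165] = Φ(0.588) = **72.2%**. With a two-sided 5% level it is 64.6%. For 80% one-sided, this formula needs 364.0/121.3, that is 364/122.

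**4. Exact calculation.** All possible tables at 276/92 were enumerated, one-sided:

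| Test | Power | True type I error |
|---|---|---|
| Fisher | 61.2% | at most 3.9% |
| Boschloo | 64.1% | at most just under 5% |
| Exact unconditional pooled z | 67.3% | at most 4.4% |
| Uncorrected chi-square, nominal 5% | 79.8% | 8.1% at a common rate of 1.5%; 10.0% at 1%; 12.3% at 0.5% |

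The maxima are over all common death rates. The uncorrected chi-square calls 1 frail death against 0 non-frail deaths significant (z = 1.734 > 1.645), where Fisher gives p = 92/368 = 0.25. A linear-programming bound over all tests of true size at most 5% gives a maximum power of **71.8%**. Fisher's test needs about 450/150 to pass 80% (80.7%).

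**5. The named regression.** Expected deaths: 276 × 0.006 = 1.66 and 92 × 0.043 = 3.96, total 5.61.
- P(no non-frail deaths) = 0.994^276 = 0.190.
- P(no frail deaths) = 0.957^92 = 0.018.
- P(either) = 1 − (1 − 0.190)(1 − 0.018) = 0.204.

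In those 20% of studies the ordinary maximum-likelihood odds ratio is not finite. Counting them as non-significant, the unadjusted logistic Wald test has 55.3% power one-sided and 40.4% two-sided. No adjusted figure is given, because the documents state no covariate effects.

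**6. Prevalence.** 92/368 = 25.0%, not 23%. At 23%, 368 patients contain 0.23 × 368 = 84.6 frail, about 283/85. Power is then 71.3% (usual formula), 55.3% (Fisher), 61.7% (Boschloo) and 67.3% (exact pooled z). Observing 92 frail patients at 23% takes 92/0.23 = 400 patients.

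**The case against.** The best defence is that 276/92 is not a slip of arithmetic. It follows from a recognisable pooled-variance shortcut, and the uncorrected one-sided chi-square, the only two-group test for categorical variables that the plan names, has exact power of 79.8% at nominal 5%. Both statements are true. They do not rescue the claim, because that power comes with a true error of 8% to 12% at common rates of 0.5% to 1.5%, and no test that keeps 5% gets above 71.8%.

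Several narrower objections have some force:

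- The 72% is itself a normal approximation, and it lies slightly above the 71.8% bound. The exact range is the firmer statement, and 364/122 would not suffice for Fisher's test.
- The plan names logistic regression, not the Wald test. The unadjusted likelihood-ratio test in the same model has 73.9% power, but with a true size of up to 10.7%. When only the non-frail group has no deaths, a likelihood-ratio p-value and a lower confidence bound still exist, so an infinite estimate does not rule out all inference.
- Sidedness is given in the Sample size section. The SAP's silence is a gap to close and not a contradiction.
- The 25% may be rounding to 3:1. The inferred shortcut at exactly 23% gives about 285/85, total 370, close to 368. The mismatch is minor, but it is unexplained.
- This is an observational cohort in which frailty assessment does not alter treatment decisions. The plan still sizes it to detect a significant difference, so its power statement should be right.

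**Conclusion.** The concern holds. At one-sided 5% and the planned rates, 276 non-frail and 92 frail patients give about 72% power by the usual formula and 61% to 67% with the exact tests examined. The chance of missing the planned difference is therefore about 28% to 39%, not 20%. The 61% to 67% range describes those three tests and not every possible test; the ceiling for any valid 5% test of the two groups is 71.8%.

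The conclusion assumes that the level written as 95% means alpha = 0.05, that the mortality rates are as planned, and that the comparison is unadjusted. The origin of 276/92 is inferred, but the conclusion does not depend on it. The 20% chance of a group without deaths depends only on the planned rates and group sizes. The 23% versus 25% mismatch and the wording of the level are secondary. This must be fixed, since the plan relies on the figure and correcting it costs very little.

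**What to change.** In the Sample size section, replace the power statement with wording such as:

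> With 276 non-frail and 92 frail patients, 90-day mortality of 0.6% versus 4.3% and a one-sided significance level of 5%, power is about 72% by the two-proportion normal formula with separate null and alternative variances, and about 61% to 67% for exact one-sided tests that hold 5%. About 5.6 deaths are expected.

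In the same paragraph:
- name the formula and the test;
- write the level as 5%;
- make the group sizes agree with 23% frailty (about 283/85 of 368, with the power figures for that split), or explain the 25%.

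In the Statistical analysis plan:
- state the sidedness of the frail versus non-frail comparison of 90-day mortality;
- name a method that holds its level and stays estimable with so few deaths. One option is an exact unconditional test for the primary comparison, with penalised-likelihood logistic regression for the odds ratio. The exact test is unadjusted, so the text should say how it relates to the adjusted model.

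The cost is one reworded paragraph and one or two SAP lines, with no added patients or data. The stated power becomes less favourable.
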